- f. Blood Chemistry consists of blood urea nitrogen (BUN), serum creatinine, creatine phosphokinase, glucose, Ca⁺⁺, Na⁺, K⁺, Cl⁻, total CO₂, aspartate aminotransferase (AST), alanine aminotransferase (ALT), total and direct bilirubin, alkaline phosphatase, uric acid, albumin, total protein, and lipid profile panel. Lipid profile panel will include total cholesterol, low-density lipoprotein (LDL), high-density lipoprotein (HDL), and triglycerides. A minimum of 8-hour fasting is required for lipid profile evaluation at Day 1, W 6, W 12, and EOS. **Laboratory tests may be repeated once during the screening period;** the last value will be used to determine eligibility.
- g. Serum pregnancy testing at screening is required for women of childbearing potential. Follicle stimulating hormone (FSH) test to be performed at Screening to confirm postmenopausal status in female subjects who have been amenorrheic for at least 12 consecutive months.
- h. Urine pregnancy test must be performed prior to dosing with the investigational product for female subjects of childbearing potential.
- i. Subjects who are positive for HIV will be screen-failed.
- j. All subjects will be screened for HBsAg and HBcAb; subjects who are HBsAg positive will be screen-failed. Subjects who are HBsAg negative but HBcAb positive will be reflex-tested for HBsAb and, if HBsAb positive, may enroll; if HBsAb negative, they will be screen-failed. Subjects who are positive for HCVAb will be screen-failed.
- k. A documented TB test performed within 12 weeks prior to Day 1 is acceptable. IGRA official reading and method, or test as per country specific guidelines, must be located in source documentation. Subjects with a history of tuberculosis may not require TB testing as per the protocol [Section 4.2](#).
- l. Pharmacokinetic samples will be collected at the following visits prior to dosing at the study site on: Week 2, 4 and 8.
- m. On Week 6, PK samples will be collected at 2 hour (±30 min) pre-dose, immediately prior to dosing, and 0.5 hour (±15 min) post dose. On Week 12, PK samples will be collected at 2 hour (±30 min) pre-dose, immediately prior to dosing, and 1 hour (±30 min), 2 hour (±30 min) and 4 hour (±30 min) post dose.

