- n. Subjects should take the medication from study Days 1 to 85. Subjects will be encouraged to take the medication after breakfast whenever it is possible. However, at study visit days, subjects are to be instructed to refrain from dosing at home, and are to take the dose in the clinic.
- o. Non-medicated study emollient and sunscreen will be provided to subjects at the Screening visit and re-supplied during the study as applicable. Subjects will start the study provided emollient 7 days prior to Day 1 through to the End of Study visit.
- p. For subjects at a selected study site(s), photographs of treatment-eligible atopic dermatitis will be obtained at Day 1 and Week 6. Areas photographed should be recorded in study documents so that the same atopic dermatitis body region(s) will be photographed at Week 6. Additional photographs may also be taken at Week 8 and/or Week 12 at the investigator's discretion.
- q. Pruritus Numerical Rating Scale (NRS) will be assessed daily from Day 1 to 15 and then at study site at every study visits.

r. CCI [REDACTED]

090177e18dabc380\0.1\Draft\Versioned On:07-Feb-2018 09:59 (GMT)

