1.5. Summary of PF-04965842 Pharmacokinetics

PF-04965842 was rapidly absorbed following single dose oral solution/suspension administration over the dose range 3 mg to 200 mg with time to maximum absorption (T_{max}) ranging between 0.55 to 0.77 hours. Median T_{max} at doses of 400 mg and 800 mg were 1.5 and 3.9 hours, respectively, which indicated the slower absorption compared to lower doses. PF-04965842 showed a monophasic decline at dose <100 mg with biphasic profiles at doses \geq 100 mg. C_{max} following the single-dose administration generally increased in proportion to the dose from 3 mg to 800 mg. In contrast, both area under the plasma concentration-time curve from time zero extrapolated to infinity (AUC_{inf}) and area under the plasma concentration time profile from time zero to the last quantifiable concentration (AUC_{last}) were dose proportional in the range of 3 mg to 200 mg, while a greater than proportional increase was observed at doses of 400 and 800 mg. The arithmetic mean terminal phase half-life ($t_{1/2}$) was 1.9 to 4.9 hours.

Following QD administration over the dose range 30 mg to 400 mg and 100 mg and 200 mg BID for 10 days, median T_{max} ranged between 0.50 to 0.77 hours. After attainment of C_{max} , the disposition of PF-04965842 was consistent with that observed following single-dose administration, showing a biphasic decline following all but the lowest dose and an arithmetic mean terminal phase $t_{1/2}$ between 2.8 to 5.0 hours. Although C_{max} generally increased in proportion to the dose up to 100 mg BID, it increased more than the dose increased at 400 mg QD and 200 mg BID. The same trend was also observed for area under the plasma concentration-time curve (AUC_{tau}) over the dosing interval ($\tau = 12$ or 24 hours). The observed accumulation ratio (R_{ac}) following 200 mg BID was 2.0 and 2.5 for AUC_{tau} and C_{max} , respectively. R_{ac} was 1.1 to 1.5 at other doses. Therefore, the results showed that drug concentration accumulation is minimal after repeated oral administration at lower doses,

consistent with the prediction from $t_{1/2}$. Urinary recovery of PF-04965842 was low, with <5% of the dose recovered unchanged in urine across all doses and regimens in all cohorts.

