1.8.2. Dose Selection Rationale

This Phase 2b study will evaluate the efficacy and safety of PF-04965842 in patients with moderate to severe AD. The study will assess 4 PF-04965842 doses of 10 mg, 30 mg, 100 mg and 200 mg administered orally once daily (QD) for 12 weeks. Listed in Table 1 are the predicted geometric mean (%CV) PK parameter values following QD dosing for 12 weeks which were derived from population PK modeling of the human PK data from the FIH study (B7451001).

Table 1. Predicted Geometric Mean PK Parameters following QD Dosing

Dose mg QD x 12 weeks	Geometric Mean		Safety Margins ^a	
	C _{max,ss} ng/mL	AUC _{tau} ng.hr/mL	C _{max,ss}	AUC _{tau}
10	33.2(9)	83.7 (33)	156	659
30	135.0 (9)	386 (36)	38	143
100	632.6 (7)	2197 (39)	8.1	25
200	1525 (6)	5928 (37)	3.4	9.3

() = % coefficient of variation; AUC_{tau} = Area under the concentration-time curve over the dosing interval 0-24 hours; C_{max,ss} = Peak plasma concentration at steady state; QD = Once daily

^a NOAEL in cynomolgus monkeys, 75 mg/kg/day; Day 273 combined male and female total C_{max,ss} = 1910 ng/mL; total AUC_{tau} = 55200 ng•h/mL.

The doses selected for this study are supported by significant safety margins from the repeat dose toxicity study up to 9 months in monkeys. The dose range should allow

characterization of the dose response for efficacy over a 20-fold range and anchoring at the lower end with a minimally effective dose.

The selective inhibition of JAK1 will lead to modulation of multiple cytokine pathways implicated in the pathophysiology of AD, eg IL-4, IL-13, IL-17, IL-22, IL-31, and INF γ . In study B7451001, mechanistic biomarkers hsCRP and IP-10 related to IL-6 and INF γ , respectively, were measured in healthy subjects.

A classic indirect response model was used to estimate the reduction of hsCRP, IP-10 and safety biomarkers (neutrophils, platelets and reticulocytes) as well as to project the potential impact on signaling of the various cytokines that may be associated with efficacy in AD over a range of PF-04965842 exposures (Table 2). The baseline values for hsCRP, IP-10 and safety biomarkers (neutrophils, platelets and reticulocytes) in subjects with AD are comparable to those observed in healthy subjects and subjects with psoriasis. The modeling predicts maximum percent reduction for the safety biomarkers in the absence of compensatory mechanism due to short duration of the studies conducted to date.

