6. STUDY PROCEDURES

Refer to the [Schedule of Activity](#) for a detailed list of a detailed list of study procedures as they should be conducted at each respective visit. Visit windows are based on Day 1 visit.

Subjects are required to fast for at least 8 hours prior to all visits that include lipid profile panel testing (Day 1, Week 6, Week 12, and EOS). During the fasting period, subjects should refrain from all food and liquids (water and non-study medications are permitted).

Due to possible need for PPD testing and chest radiograph, screening procedures may be performed over more than 1 visit in the 35 days prior to the Day 1 visit.

Visits should occur in the morning and prior to the subject's dose on Day 1, Week 6, Week 12, and EOS. To assure consistency and reduce variability, all study visits should occur in the morning whenever possible. On days of study visits, subjects will receive their dose at the clinic during their study visit.

Urine pregnancy test must be performed prior to dosing with the investigational product for female subjects of childbearing potential through to the EOS visit.

Non-medicated study emollient and sunscreen will be provided to subjects at the Screening Visit and re-supplied during the study as applicable. Prior to attending a study visit, subjects are allowed to shower but should not moisturize. However, they may apply study provided emollient upon completion of all clinic visit study procedures. Subjects will start the study provided emollient 7 days prior to Day 1 through to the EOS visit.

Refer to [Appendix 11](#) for guidelines on subject safety monitoring and discontinuation.

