6.2.7. Visit 8, Day 85/Week 12 (± 3 day)

- Conduct complete physical examination.
- Obtain vital signs including pulse rate, blood pressure, respiratory rate (after at least 5 minutes of rest) and oral or tympanic temperature.
- Obtain **fasting** samples for blood chemistry including lipid profile.
- Obtain samples for laboratory testing: hematology, urinalysis, urine pregnancy test (female subjects of childbearing potential only), EBV, CMV, HSV1, HSV2, VZV, IgE, hsCRP, IP-10, IL-31, CCL17, TBNK, T cell subsets, and exploratory biomarker samples.
- **Prior to dosing**, obtain samples for PK analysis (the first PK sample is to be collected 2 hours (± 30 minutes) prior to dosing; the second PK sample is to be collected immediately prior to dosing).
- Photography at selected sites (at PI's discretion).
- Conduct clinical evaluations including IGA, EASI, BSA, and SCORAD.
- Administer PROs including Pruritus NRS, PtGA, DLQI, POEM, and HADS.
- Review **CCI** (in selected country/ies) as necessary.
- Perform single 12-lead ECG.

- Confirm proper contraception is being used.
- Review any changes in the subject's concomitant treatments information.
- Perform drug accountability procedures.
- Administer study drug to the subject.
- Obtain samples for PK analysis at 1 hour (± 30 minutes), 2 hour (± 30 minutes), and 4 hour (± 30 minutes), after dosing.
- Assess for occurrence of Adverse Events by spontaneous reporting of adverse events and by asking the subjects to respond to a non-leading question such as "How do you feel?"

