7.3.4. Electrocardiogram

Single 12-lead ECGs should be collected at times specified in the [Schedule of Activities](#).

All scheduled ECGs should be performed after the subject has rested quietly for at least 10 minutes in a supine position and prior to any blood collection.

The screening ECG values will serve as each subject's baseline values. To ensure safety of the subjects, a qualified individual (eg sub-investigator) at the investigator site will make comparisons to baseline measurements. A paper or digital copy of the ECG should be filed

in the subject's chart and must be available to the Sponsor upon request. Any clinically significant changes will be recorded and evaluated further, as clinically warranted. In some cases, it may be appropriate to repeat abnormal ECGs to rule out improper lead placement as contributing to the ECG abnormality.

7.3.5. QuantiFERON[®] - TB Gold In-Tube Test and Mantoux/Purified Protein Derivative (PPD) Tuberculin Skin Test

QuantiFERON[®] - TB Gold In-Tube is an in vitro diagnostic test using a peptide cocktail simulating ESAT-6, CFP-10 and TB 7.7 proteins to stimulate cells in heparinized whole blood. Detection of interferon-gamma by Enzyme-Linked Immunosorbent Assay (ELISA) is used to identify in vitro responses to these peptide antigens that are associated with *Mycobacterium tuberculosis* infection. QuantiFERON[®] - TB Gold In-Tube is an indirect test for *M. tuberculosis* infection (including disease) and is intended for use in conjunction with risk assessment, radiography and other medical and diagnostic evaluations.

Test results will be reported as positive, negative or indeterminate. In the case of an indeterminate result, repeat tests may be permitted for the purpose of determining eligibility of subjects to enroll in this study. It is recommended that subjects with a history of BCG vaccination be tested with the QFT-G test since the Mantoux/PPD tuberculin skin test may be positive due to vaccination. A positive QFT-G test is exclusionary. The procedure for using this test and interpreting the results will be described fully in the laboratory manual, which will be provided to investigators.

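### The only routine on-treatment ECG (Week 12) is recorded before the clinic dose, so the scheduled ECGs cannot show an effect tied to peak concentration

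*Protocol*

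**What the plan says.** The Schedule of Activities places 12-lead ECGs at Screening, Day 1, Week 12 and Week 16 (End of Study or early termination). Section 7.3.4 says these are single recordings, made after 10 minutes of supine rest and "in a supine position and prior to any blood collection".

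Four provisions fix when the Week 12 recording falls relative to the dose:

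- Section 6: "Visits should occur in the morning and prior to the subject's dose on Day 1, Week 6, Week 12, and EOS".
- Schedule of Activities, footnote n, on visit days: "subjects are to be instructed to refrain from dosing at home, and are to take the dose in the clinic".
- Section 6.2.7: "the first PK sample is to be collected 2 hours (± 30 minutes) prior to dosing". Footnote m agrees, and adds draws at 1, 2 and 4 hours after the dose.
- The checklist in Section 6.2.7 puts the ECG after the pre-dose blood samples, which does not match Section 7.3.4, but before study drug is given.

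On exposure, Section 1.5 reports that median Tmax on repeat dosing "ranged between 0.50 to 0.77 hours", with a mean terminal half-life of 2.8 to 5.0 hours.

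On baseline, Section 7.3.4 states: "The screening ECG values will serve as each" subject's baseline. SAP Appendix 1 sets baseline at relative day 1, allows the last observation up to first dosing if Day 1 is missing, and applies its visit windows to safety displays by week.

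**The concern.** Of the four scheduled ECGs, two precede any exposure and one is nominally 28 days after the last dose (Day 113 minus Day 85). That leaves Week 12, and it is a trough recording of a drug that peaks within an hour and has a short half-life.

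Safety across a 20-fold dose range is a stated objective, and Section 9.3 names ECG parameters, where applicable, among the safety data. If the Week 12 ECGs look alike across the arms, the result could be read as cardiac reassurance at 200 mg although no scheduled ECG was made near peak exposure. Yet at that same visit the patient stays in clinic for blood draws up to 4 hours after dosing, so a recording at higher exposure is within reach.

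**Working it through.** The documents give neither the time from dose to ECG nor the concentration at the ECG, so there is no stated figure to reproduce. Both are derived here.

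**Step 1: time since the previous dose.** Section 1.8.2 has the drug "administered orally once daily (QD) for 12 weeks", a nominal interval of 24 h. The first Week 12 draw is 2 h (±0.5 h) before the dose, and Section 7.3.4 puts the ECG before it.

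- Latest ECG time that obeys 7.3.4 = 24 − 2 = 22 h after the previous dose (21.5 to 22.5 h over the window).
- If the ECG follows the draws, as the 6.2.7 checklist has it, the time runs up to about 24 h. Either order is pre-dose.

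**Step 2: residual concentration.** Fraction of peak = 2^(−(t − Tmax)/t½), with t½ of 2.8 to 5.0 h and Tmax of 0.50 to 0.77 h from Section 1.5.

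| Hours after previous dose | t½ = 2.8 h | t½ = 5.0 h |
|---|---|---|
| 12 (dose taken the evening before) | 5.8–6.2% | 20.3–21.1% |
| 21.5 | 0.55–0.59% | 5.4–5.7% |
| 22 | 0.49–0.52% | 5.1–5.3% |
| 22.5 | 0.43–0.46% | 4.7–4.9% |
| 24 (ECG after the draws) | 0.30–0.32% | 3.9–4.0% |

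With Tmax set at 0.6 h, the 21.5 to 22.5 h range is 0.4% (2^(−21.9/2.8)) to 5.5% (2^(−20.9/5.0)). At 200 mg, where Table 1 predicts a steady-state peak of 1525 ng/mL, the 22 h level is about 7 to 80 ng/mL.

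**Step 3: cross-checks from Table 1 (200 mg).**

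- Effective half-life = ln 2 × AUCtau/Cmax = 0.693 × 5928/1525 = 2.7 h. This gives about 6 ng/mL at 22 h, or 0.4% of peak.
- A bound that needs no half-life: if concentration only falls after the peak, the 22 h level cannot exceed AUCtau divided by the time since peak. That is 5928/21.2 ≈ 280 ng/mL, or 18% of peak. The same bound is about 12% to 16% at the lower doses.

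**Step 4: the post-dose PK times already scheduled.** Taking Tmax as 0.5 h, the same formula gives 88–93% of peak at 1 h, 69–81% at 2 h and 42–62% at 4 h. These are approximate. The documents give no tablet Tmax, although Section 5.4.1 supplies tablets, and each draw has a ±30 min window.

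**The case against.** The strongest case against is that Section 7.3.4 describes a clinical check on the individual, not an exposure-response study. The formal safety endpoints in Section 2.4.2.2 are adverse events and specified laboratory abnormalities. Section 9.3 qualifies ECG parameters as applying only where applicable, and SAP Section 8.2.3 describes no ECG analysis. That stands. A reader might infer that a planned dose comparison of ECGs is invalidated, but no such comparison is specified.

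A reader might also infer that the trial cannot detect any exposure-related ECG effect. The documents do not support that. A sustained or delayed effect, or one from a longer-lived metabolite, could show at trough. Section 7.3 allows unscheduled safety assessments at any time. The early-termination visit carries an ECG whose time from the last dose is not fixed.

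The size also has limits:

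- The 22 h figure assumes a 24 h interval, while dosing after breakfast is only encouraged.
- Decline is biphasic at all but the lowest repeated dose, so running the terminal half-life from the peak tends to overstate what remains.
- The observed accumulation ratios of 1.1 to 1.5 exceed the 1.00 to 1.04 that these half-lives predict for once-daily dosing. Read as pure carry-over, they would imply about 12% to 37% of peak at 22 h. That conflicts with the stated half-lives, and its upper end exceeds the Table 1 bound. Non-linear kinetics, which Section 1.5 reports at higher doses, is the likelier reason.

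There is earlier ECG experience. Phase 1 went up to 800 mg as a single dose and 400 mg per day repeated. For the 800 mg and 200 mg BID cohorts, Section 1.4.2.1.1 reports no ECG abnormality judged clinically significant. The timing of those ECGs is not given, so this lowers the urgency without settling the matter.

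**Conclusion.** The point holds for one recording and one kind of effect. The Week 12 ECG is pre-dose under either reading of the visit order. With 24 h dosing it falls about 22 h after the previous dose, at roughly 0.4% to 5.5% of peak. If the previous dose was taken the evening before, the figure is about 6% to 21%, still far from peak. The scheduled ECGs therefore cannot show an effect tied to peak concentration, and a clean result should not be cited as evidence about peak exposure. The percentages rest on the half-life and Tmax in Section 1.5 and on a single-exponential decline. The conclusion that the ECG is pre-dose rests on the visit provisions alone.

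A reader might want a fold-difference between the present ECG and one at 1 h. The documents do not support a firm ratio without a tablet Tmax.

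On baseline, a reader might infer that no sound pre-dose baseline exists. One does: a Day 1 pre-dose ECG is collected, and SAP Appendix 1 points to it for by-week safety displays. What remains is a conflict between protocol and SAP. This is a low-cost improvement, not a flaw that undermines the trial.

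**What to change.** In Section 7.3.4, Section 6.2.7 and the Schedule of Activities:

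- Move the existing Week 12 ECG to a post-dose time at which the patient is already in clinic for PK, for example just before the 1-hour draw, keeping the 10-minute supine rest.
- Exempt that ECG from the rule on preceding blood collection, as far as the earlier draws that day are concerned. This also removes the mismatch in order between 7.3.4 and 6.2.7.
- If a pre-dose recording is intended, say so in 7.3.4 and state that the ECG data describe trough exposure only.
- Use the Day 1 pre-dose ECG as baseline in 7.3.4, with the last earlier recording as backup, to match SAP Appendix 1.

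The cost is a wording change, with no added ECG, visit or clinic time. There are two small downsides. The ECG would follow earlier venepuncture, which the rest period helps with. A post-dose recording would also be compared with a fasting pre-dose baseline. The placebo arm controls for that between groups, but not in the individual check made at the site.

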 10. Have active chronic or acute skin infection (except latent TB infection see Exclusion Criterion [20](#)) requiring treatment with systemic antibiotics, antivirals, antiparasitics, antiprotozoals, or antifungals within 2 weeks prior to Day 1, or superficial skin infections within 1 week prior to Day 1. NOTE: patients may be rescreened after infection resolves.

11. Have a history of alcohol or substance abuse within 6 months prior to Day 1 that in the opinion of the investigator will preclude participation in the study.
12. A Screening 12-lead ECG that demonstrates clinically significant abnormalities requiring treatment (eg, acute myocardial infarction, serious tachy- or brady-arrhythmias) or that are indicative of serious underlying heart disease (eg, cardiomyopathy, major congenital heart disease, low voltage in all leads, Wolff–Parkinson–White syndrome).
13. Have a known immunodeficiency disorder or a first-degree relative with a hereditary immunodeficiency.
14. Have any malignancies or have a history of malignancies with the exception of adequately treated or excised non-metastatic basal cell or squamous cell cancer of the skin or cervical carcinoma in situ.
15. Have undergone significant trauma or major surgery within 1 month of the first dose of study drug.
16. Require treatment with prohibited concomitant medication(s) ([Section 5.8](#) and [Appendix 3](#)) or have received a prohibited concomitant medication within 7 days or 5 half-lives (whichever is longer) prior to Day 1.
17. History of human immunodeficiency virus (HIV) or positive HIV serology at screening,
18. Infected with hepatitis B or hepatitis C viruses. For Hepatitis B, all subjects will undergo testing for Hepatitis B Surface Antigen (HBsAg) and Hepatitis B Core Antibody (HBcAb). Subjects who are HBsAg positive are not eligible for the study. Subjects who are HBsAg negative and HBcAb positive will be reflex tested for Hepatitis B Surface Antibody (HBsAb) and if HBsAb is positive, may be enrolled in the study; if HBsAb is negative, the subject is not eligible for the study.
19. Have evidence of active or latent or inadequately treated infection with Mycobacterium tuberculosis (TB) as defined by the following:

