6.1. Visit 1, Screening

Subjects will be screened within 35 days prior to administration of the investigational product to confirm that they meet the subject selection criteria for the study. The investigator (or an appropriate delegate at the investigator site) will obtain informed consent from each subject in accordance with the procedures described in the [Subject Information and Consent](#) section.

If the Mantoux PPD tuberculin skin test is given, the subject must return between 48-72 hours post-injection for induration evaluation.

Screening laboratory tests with abnormal results may be repeated once to confirm abnormal results; the last value will be used to determine eligibility. If results return to normal within the 5-week screening period, the subject may enter the study. Sites will be permitted to re-screen subjects (with a new screening number) who initially do not meet eligibility criteria once.

The following procedures will be completed:

- Obtain written informed consent.
- Review Inclusion and Exclusion criteria.
- Register subject in Impala.
- Demography.
- Complete medical history, including history of drug, alcohol and tobacco use. Smoking status and average weekly alcohol consumption (units/week) will also be collected, where a unit contains 12 g of pure alcohol, an amount equivalent to that contained in 5 oz (a glass) of wine, 12 oz of beer, or 1.5 oz of 90 proof of spirits.
- Complete AD disease history includes collection of details of AD: AD diagnosis, the use of topical treatments, systemic treatments and other treatments for AD.
- Obtain complete medication history of all prescription or nonprescription drugs, and dietary and herbal supplements taken within 35 days prior to the planned first dose.

The following timeframes prior to the planned first dose must be used for collection of the following Current/Prior Medications:

- 2 years: Lipid-lowering medications;
- 3 years: Previous drug treatments for AD includes use of topical treatments, systemic treatments and other any treatments.

- Conduct complete physical examination.
- Obtain vital signs including pulse rate, blood pressure, respiratory rate (after at least 5 minutes of rest) and oral or tympanic temperature.
- Obtain weight
- Obtain height.
- Chest X-ray (if previous chest X-ray has not been performed within 12 weeks of Day 1, may require a visit to a different location).
- Perform single 12-lead electrocardiogram (ECG).

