6.2. Study Period

6.2.1. Visit 2, Day 1/Week 0

- Review of Inclusion/Exclusion Criteria.
- If subject meets all Inclusion/Exclusion criteria, officially randomize subject into the study.
- Review any changes in the subject's prior and concomitant treatment information.
- Obtain vital signs including pulse rate, blood pressure, respiratory rate (after at least 5 minutes of rest) and oral or tympanic temperature.
- Obtain weight.

- Conduct complete physical examination.
- Obtain **fasting** samples for blood chemistry including lipid profile.
- Obtain samples for other laboratory testing: hematology, urinalysis, urine pregnancy test (female subjects of childbearing potential only), EBV, CMV, HSV1, HSV2, VZV, IgE, hsCRP, IP-10, IL-31, CCL17, TBNK, T cell subsets, and exploratory biomarker samples.
- Perform Fitzpatrick skin type assessment.
- Photography (at selected sites).
- Conduct clinical evaluations including IGA, EASI, BSA, and SCORAD.
- Administer PROs including Pruritus NRS, PtGA, DLQI, POEM, and HADS.

Note: The Pruritus NRS will be assessed daily from Day 1 to 15.

- Review CCI (in selected country/ies) as necessary.
- Perform single 12-lead ECG.
- Obtain Prep D1 sample for banked biospecimen pharmacogenomics testing.
- Confirm proper contraception is being used.
- Administer first dose of study drug to subject.
- Dispense study drug supply to the subject.
- Assess for occurrence of Adverse Events by spontaneous reporting of adverse events and by asking the subjects to respond to a non-leading question such as “How do you feel?”

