10. APPENDICES

Appendix 1. DEFINITION AND USE OF VISIT WINDOWS IN REPORTING

Note Day 1 in the table below is taken as the first day of dosing with study drug. It may not be the same as the first study date which is the randomization date. Also note that Day 0 does not exist, so Day -1 is the day before Day 1. Also the relative days (rel_day) from Day 1 are defined as the visit date minus first dosing date plus one.

Visit windows will be used for efficacy variables, and for any safety displays that display by week.

Table 1. Visit Window Definition for Analysis (update wider visit windows)

Visit No.	Visit Label	Target Day	Visit Window
1	Screening	N/A	-35≤rel_day≤-1
2	Baseline*	1	Rel_day= 1
3	Week 1	8	2≤rel_day≤11
4	Week 2	15	12≤rel_day≤22
5	Week 4	29	23≤rel_day≤36
6	Week 6	43	37≤rel_day≤50
7	Week 8	57	51≤rel_day≤71
8	Week 12	85	72≤rel_day≤88
9	Week 13	92	89≤rel_day≤95
10	Week 14	99	96≤rel_day≤106
11	Week 16	113	107≤rel_day≤120

* Baseline analysis visit window may be considered as Rel_day≤1 in some analyses (eg, those involving change from baseline). That is, in case that Day 1 observation is missing, the last observation by the first dosing date may be considered as the baseline.

090177e18dabc776\0.1\Draft\Versioned On:07-Feb-2018 10:11 (GMT)

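### The ECG baseline is the screening tracing, up to 35 days old and possibly recorded before washout of prohibited drugs, although a Day 1 ECG before the first dose is already scheduled

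*Protocol*

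**What the plan says.** Protocol 7.3.4 fixes the reference tracing: "The screening ECG values will serve as each" subject's baseline. It gives the purpose as subject safety: a qualified person "at the investigator site will make comparisons to baseline measurements".

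On timing, Protocol 6.1 states: "Subjects will be screened within 35 days prior to administration of the investigational product". The Schedule of Activities marks ECGs at screening, Day 1, Week 12 and Week 16 or early termination. The Day 1 list in Protocol 6.2.1 includes "Perform single 12-lead ECG" and, further down, "Administer first dose of study drug to subject". Section 6 adds "Visits should occur in the morning and prior to the" subject's dose on Day 1 and other named visits.

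On washout, Exclusion 16 bars subjects who need a prohibited drug or who "have received a prohibited concomitant medication within 7 days or 5 half-lives (whichever is longer) prior to Day 1". Protocol 5.8 itself treats the time between consent and first dose as a combined screening and washout period.

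On reporting, SAP Appendix 1 places baseline at relative day 1 and allows an earlier value when Day 1 is missing. Its scope is: "Visit windows will be used for efficacy variables, and for any safety displays that display by week".

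**The concern.** A baseline should describe the subject just before treatment, under the conditions in which treatment starts. The screening ECG can miss on both counts. It may be several weeks old, and it may have been recorded on a drug that then had to be stopped. Appendix 3 lists cardiac drugs, including diltiazem, verapamil and amiodarone. If stopping such a drug moves an ECG interval or the heart rate, a comparison with screening mixes that shift with any effect of study drug. Inclusion 7 adds to this: other concomitant medication need be stable only for the longer of 7 days and 5 half-lives before Day 1, so it too can change after the screening ECG.

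The Day 1 tracing falls after both limits and is already collected. Under 7.3.4 it serves only as the first follow-up reading. What is at stake is the reading of individual subjects' ECG changes and of any ECG change-from-baseline table. No efficacy result depends on it.

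**Working it through.** The plan gives no figure of its own here, so the check is day arithmetic and a comparison of sections.

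**Age of the reference ECG.** Inputs: screening Days -35 to -1; first dose Day 1; Week 12 = Day 85 ± 3; Week 16 = Day 113 ± 3 (Schedule of Activities). There is no Day 0 (SAP Appendix 1), so the elapsed time from Day -a to Day b is a + b - 1.

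| Point | Oldest screening ECG | Day 1 ECG |
|---|---|---|
| First dose | 35 + 1 - 1 = 35 days | 0 days |
| Week 12 | 35 + 85 - 1 = 119 (122 with window) | 84 (87) |
| Week 16 | 35 + 113 - 1 = 147 (150 with window) | 112 (115) |

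A screening ECG on Day -1 is 1 day old at first dose, so the range is 1 to 35 days.

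**Overlap with permitted use of prohibited drugs.** Let w be the required drug-free time before Day 1, the larger of 7 days and 5 half-lives. The screening days before the latest permitted stop date number 35 - w, or none if w is 35 or more.

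- With w = 7: 35 - 7 = 28 days, Day -35 to Day -8.
- The half-life rule takes over when the half-life exceeds 7 / 5 = 1.4 days, and the overlap then shrinks.
- With a half-life of 35 / 5 = 7 days or more there is no overlap, because the drug must be stopped before screening opens.

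The documents give no half-lives, so 28 days is the maximum and not a typical value.

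**Is the Day 1 ECG before the dose?** No ECG line says so outright. Three rules point the same way: the ECG precedes the first dose in the 6.2.1 list, Section 6 places the Day 1 visit before dosing, and 7.3.4 requires ECGs before any blood is drawn.

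**Does any planned output use an ECG baseline?**

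- Protocol 9.3 lists ECG parameters only where applicable, and plans change-from-baseline summaries for laboratory data and vital signs.
- The safety endpoints in Protocol 2.4.2.2 and SAP 6.1.2.4 do not include ECG.
- SAP 8.2.3 names outputs for adverse events, laboratory parameters and vital signs, not ECG.
- SAP Appendix 1 reaches ECG only if an ECG display by week is produced. Baseline would then be Day 1, against screening in 7.3.4.

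**The case against.** The best defence is that 7.3.4 describes site safety review, not an analysis. The screening ECG is the tracing on which Exclusion 12 judges eligibility, so it is a natural reference, and it lets the site compare the Day 1 ECG with it before dosing. Exclusion 16 also removes anyone who requires a prohibited drug, while Exclusions 6 and 12 remove significant cardiac disease and significant ECG abnormality. The group who could stop such a drug during screening may be small, and the documents give neither its size nor any ECG effect.

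Much of this stands, and it rules out four stronger readings that a reader might infer:

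- **That the protocol and SAP already conflict on ECG.** They do not. One rule is specific to ECG; the other is a general visit-window rule that applies only if ECG is displayed by week.
- **That the active-placebo comparison is biased.** Washout happens before randomised treatment starts, so any shift is expected to be equal across arms.
- **That ECG is a firm safety endpoint.** Protocol 9.3 lists it conditionally.
- **That moving to Day 1 improves precision.** With one reading at each time, independent errors and equal variance s², the variance of a change is s² + s² = 2s² under either baseline. The case for Day 1 rests on recency, washout and consistency.

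The defence does not explain why individual changes should be measured from the older tracing when a later one before dosing exists. The screening ECG can keep its eligibility role either way.

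**Conclusion.** The point holds and is minor. Protocol 7.3.4 selects a baseline ECG that can be 35 days older than the available alternative. With the 7-day minimum, up to 28 of the 35 screening days allow it to be recorded while a prohibited drug is still being taken. The consequence lies in within-subject comparisons and in any ECG change summary that may be produced. The difference between site and report baselines is conditional on ECG being tabulated by week.

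The conclusion assumes that the Day 1 ECG is taken before dosing, as the visit rules imply, and that some subjects stop a prohibited drug after their screening ECG. It also assumes that stopping such a drug can alter an ECG. How many subjects are affected, and by how much, cannot be estimated from the documents.

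**What to change.** - In Protocol 7.3.4, define the baseline for ECG change-from-baseline comparisons and summaries as the Day 1 pre-dose ECG for every subject. Use the last earlier pre-dose ECG if Day 1 is missing. State that the screening ECG is kept for eligibility.
- In Protocol 6.2.1, mark the Day 1 ECG as pre-dose, so that this no longer rests on inference.
- In the SAP (Appendix 1 or 8.2.3), give the same definition and say whether ECG change will be tabulated and at which visits. Relative day 1 alone does not separate readings before and after the dose.

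Use one definition for all subjects, whatever their medication history. The cost is about one sentence in each place, with no extra recording. Appendix 11 has no ECG discontinuation threshold, so no stopping rule changes, and how investigators act on an ECG finding is not affected.
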